8.2 Objective 2: Effectiveness Outcomes

8.2.1 Endpoint Data

Real world Overall Survival

Table 15.2.1.19. Kaplan-Meier Analysis of rwOS from Start of 1L Using Regimen-Based Lines of Therapy

OS	palbociclib + AI (n=xxx)
No. of Events/No. of Patients	xxx/xxx
No. of Censored	xx
Minimum, Maximum	xx.x, xx.X
Kaplan-Meier Estimates in months (95% CI)	
25 th percentile	xx.x (xx.x, x,x)
Median	xx.x (xx.x, x,x)
75 th percentile	xx.x (xx.x, x,x)

Figure 15.2.1.2. Kaplan-Meier Analysis of rwOS

Table 15.2.1.3. Cox Model for Assessing Factors Associated with rwOS from Start of 1L

Parameters	Estimate	Std Error	HR	95% CI for HR	P-Value
Age in years (≥ 75 vs <50)	x.xxx	x.xxx	x.xxx	x.xxx-x.xxx	x.xxxx
Age in years (65-74 vs <50)	x.xxx	x.xxx	x.xxx	x.xxx-x.xxx	x.xxxx
Age in years (50-64 vs <50)	x.xxx	x.xxx	x.xxx	x.xxx-x.xxx	x.xxxx
Race (Black or African American vs White)	x.xxx	x.xxx	x.xxx	x.xxx-x.xxx	x.xxxx
Race (Other vs White)	x.xxx	x.xxx	x.xxx	x.xxx-x.xxx	x.xxxx
ECOG/KPS (≥ 2 vs 0)	x.xxx	x.xxx	x.xxx	x.xxx-x.xxx	x.xxxx
ECOG/ KPS (1 vs 0)	x.xxx	x.xxx	x.xxx	x.xxx-x.xxx	x.xxxx
Menopausal status (post vs pre or peri)	x.xxx	x.xxx	x.xxx	x.xxx-x.xxx	x.xxxx
Metastatic group (de novo vs recurrent)	x.xxx	x.xxx	x.xxx	x.xxx-x.xxx	x.xxxx
Stage at Diagnosis (IV vs 0 or I)	x.xxx	x.xxx	x.xxx	x.xxx-x.xxx	x.xxxx
Stage at Diagnosis (III vs 0 or I)	x.xxx	x.xxx	x.xxx	x.xxx-x.xxx	x.xxxx
Stage at Diagnosis (II vs 0 or I)	x.xxx	x.xxx	x.xxx	x.xxx-x.xxx	x.xxxx

PFIZER CONFIDENTIAL

Table 15.2.1.3. Cox Model for Assessing Factors Associated with rwOS from Start of 1L

Parameters	Estimate	Std Error	HR	95% CI for HR	P-Value
Number of disease sites (≥ 3 vs 1)	x.XXX	x.XXX	x.XXX	x.XXX-x.XXX	x.XXXX
Number of disease sites (2 vs 1)	x.XXX	x.XXX	x.XXX	x.XXX-x.XXX	x.XXXX
Time from initial diagnosis to metastasis (≤ 36 vs > 36 months)	x.XXX	x.XXX	x.XXX	x.XXX-x.XXX	x.XXXX
Visceral disease (Yes vs No)	x.XXX	x.XXX	x.XXX	x.XXX-x.XXX	x.XXXX
Prior endocrine therapy (Yes vs No)	x.XXX	x.XXX	x.XXX	x.XXX-x.XXX	x.XXXX
Prior chemotherapy (Yes vs No)	x.XXX	x.XXX	x.XXX	x.XXX-x.XXX	x.XXXX
Prior surgery (Yes vs No)	x.XXX	x.XXX	x.XXX	x.XXX-x.XXX	x.XXXX
Prior radiation therapy (Yes vs No)	x.XXX	x.XXX	x.XXX	x.XXX-x.XXX	x.XXXX

Table 15.2.1.4. Kaplan-Meier Analysis of rwOS from Start of 1L Using Regimen-Based Lines of Therapy for Patients who Received 125mg Starting Dose**Figure 15.2.1.5. Kaplan-Meier Analysis of rwOS for Patients who Received 125mg Starting Dose**

Table shells for the following analysis can be repeated as displayed above-

Real world Progression free Survival

Table 15.2.2.1. Kaplan-Meier Analysis of time to rwPFS from Start of 1L Using Regimen-Based Lines of Therapy**Figure 15.2.2.2. Kaplan-Meier Analysis of rwPFS****Table 15.2.2.3. Cox Model for Assessing Factors Associated with time to rwPFS from Start of 1L****Table 15.2.2.4. Progression Details After Start of 1L Therapy for A/MBC Diagnosis****Table 15.2.2.5. Kaplan-Meier Analysis of time to rwPFS from Start of 1L Using Regimen-Based Lines of Therapy by Metastasis Status****Figure 15.2.2.6. Kaplan-Meier Analysis of rwPFS by Metastasis Status**

Table 15.2.2.7. Kaplan-Meier Analysis of time to rwPFS from Start of 1L Using Regimen-Based Lines of Therapy for Patients who Received 125mg Starting Dose

Figure 15.2.2.8. Kaplan-Meier Analysis of rwPFS for Patients who Received 125mg Starting Dose

Real world time to discontinuation

Table 15.2.3.1 Kaplan-Meier Analysis of time to rwTTD from Start of 1L Using Regimen-Based Lines of Therapy

Figure 15.2.3.2. Kaplan-Meier Analysis of rwTTD

Table 15.2.3.3. Cox Model for Assessing Factors Associated with time to rwTTD from Start of 1L

Table 15.2.3.4 Kaplan-Meier Analysis of time to rwTTD from Start of 1L Using Regimen-Based Lines of Therapy for Patients who Received 125mg Starting Dose

Figure 15.2.3.5 Kaplan-Meier Analysis of rwTTD for Patients who Received 125mg Starting Dose

Real world time to next treatment

Table 15.2.4.1. Kaplan-Meier Analysis of time to rwTTNT from Start of 1L Using Regimen-Based Lines of Therapy

Figure 15.2.4.2. Kaplan-Meier Analysis of time to rwTTNT

Table 15.2.4.3. Cox Model for Assessing Factors Associated with time to rwTTNT from Start of 1L

Table 15.2.4.4. Kaplan-Meier Analysis of time to rwTTNT from Start of 1L Using Regimen-Based Lines of Therapy for Patients who Received 125mg Starting Dose

Figure 15.2.4.5. Kaplan-Meier Analysis of time to rwTTNT for Patients who Received 125mg Starting Dose

Real world time to Chemotherapy

Table 15.2.5.1. Kaplan-Meier Analysis of time to rwTTC from Start of 1L Using Regimen-Based Lines of Therapy

Figure 15.2.5.2. Kaplan-Meier Analysis of time to rwTTC

Table 15.2.5.3. Cox Model for Assessing Factors Associated with time to rwTTC from Start of 1L

Table 15.2.5.4. Kaplan-Meier Analysis of time to rwTTC from Start of 1L Using Regimen-Based Lines of Therapy for Patients who Received 125mg Starting Dose

Figure 15.2.5.5. Kaplan-Meier Analysis of time to rwTTC for Patients who Received 125mg Starting Dose

Real world time to Dose Adjustment

Table 15.2.6.1. Kaplan-Meier Analysis of time to rwTTDA from Start of 1L Using Regimen-Based Lines of Therapy

Figure 15.2.6.2. Kaplan-Meier Analysis of time to rwTTDA

Table 15.2.6.3. Cox Model for Assessing Factors Associated with time to rwTTDA from Start of 1L

Table 15.2.6.4. Kaplan-Meier Analysis of time to rwTTDA from Start of 1L Using Regimen-Based Lines of Therapy for Patients who Received 125mg Starting Dose

Figure 15.2.6.5. Kaplan-Meier Analysis of time to rwTTDA for Patients who Received 125mg Starting Dose

Note-Each efficacy outcome will be analyzed as per the timepoints defined in section 5.

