 - c. Real-world time to treatment discontinuation (rwTTD) from the start of the first-line therapy at time points 3, 6, 12, 18, 24, 30, and 36 months.
 - d. Real-world time to next treatment (rwTTNT) from the start of the first-line therapy at time points 3, 6, 12, 18, 24, 30, and 36 months.
 - e. Real-world time to chemotherapy (rwTTC) from the start of the first-line therapy at time points 3, 6, 12, 18, 24, 30, and 36 months.
 - f. Real-world time to dose adjustment (rwTTDA) from the start of the first-line therapy at time points 3, 6, 12, 18, 24, 30, and 36 months.

5.1 Definitions/Derivations for Demographic, Clinical characteristics, treatment pattern and Efficacy/Effectiveness Endpoint(s)

- Age at initial diagnosis, A/MBC diagnosis, at start of palbociclib treatment and death. - They will be categorized into age categories: <50, 50-64, 65 –74, ≥75 years.
- Time to metastasis- It is defined as months between initial and metastasis diagnoses. It will be categorized into ≤12 months, 13-24 months, 25-36 months,>36 months and de novo metastatic.
- Disease Free Interval (DFI)- It is defined as months from the end of adjuvant therapy to the date of disease recurrence. It will be categorized into ≤12 months, 13-24 months, 25-36 months,>36 months and Unknown.
- Line of therapy- The line number (1; 2; 3; etc.) in the A/MBC setting will be assigned based on Syapse line of therapy algorithm.
- Regimen medication(s)- Systemic therapies included in line regimen defined by Syapse line of therapy algorithm.
- Time to first dose change- It is defined as days from palbo dose 1 start date to palbo dose 2 start date, if applicable.
- Number of dose changes- Number of dose reduction(s) and number of dose increases over the calendar time (quarter since February 2015) and over treatment cycle since palbo dose 1 start date.
- Real-world Overall Survival (rwOS)- It is defined as length of time from the start of palbociclib + AI treatment to the earliest of the following: date of death, date of last contact, or the end of study period
- Real-world progression free survival (rwPFS)- It is defined as length of time from the start of palbociclib + AI treatment to the earliest of the following: clinician-assessed progression event (sources include medical oncology consult/note, radiation oncology note and discharge summary), date of death, date of initiation

PFIZER CONFIDENTIAL

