7 STATISTICAL METHODOLOGY AND STATISTICAL ANALYSES

7.1 Statistical methods

Descriptive analyses: For categorical variables (eg region, race, and stage at initial diagnosis), data will include the frequency (number of cases) and percentage (%) of total patients observed in each category; for continuous variables (eg age and time from initial breast cancer diagnosis to metastatic diagnosis), variables will be presented as the mean, standard deviation (SD), median, 25th and 75th percentiles and ranges (minimum and maximum) in some cases. The calculation of percentages will always include the missing category in the case of missing values. Continuous variables may be categorized into intervals, with the distribution of patients (N, %) provided.

Kaplan-Meier curves and landmark analyses will be performed to estimate rwPFS, rwOS, rwTTD, rwTTC, rwTTDA and rwTTNT. Specifically, landmark time points are; 3, 6, 12, 18, 24, 30, and 36 months for rwPFS and 6, 12, 18, 24, 30, and 36 months for rwOS. For rwTTD and rwTTNT, landmark time points are; 3, 6, 12, 18, 24, 30, and 36 months. Ninety-five percent confidence intervals on the median rwPFS, rwOS, rwTTD, rwTTNT, rwTTC and rwTTDA will be reported.

Cox proportional hazard models may include age categories, race, ECOG performance, menopausal status, stage at initial diagnosis, time from initial diagnosis to metastatic diagnosis, metastatic status (De novo, versus number of metastatic sites), number of disease sites (1, 2, ≥ 3), prior endocrine therapy, prior chemotherapy, prior surgery, prior radiation therapy, bone-only disease, presence of visceral disease, and presence of brain metastases as appropriate based on availabilities of the data and sample sizes. Potential interactions may be examined using survival trees for time to events.

All data analysis will be executed using statistical software R version 3.6.1 or later.

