One Kaplan-Meier analysis is generated for each time to event endpoint. Kaplan-Meier analysis will include number of patients with events and censored patients, median, 25th percentile and 75th percentile times to event (in months), 95% CI of the quartiles and ranges (minimum and maximum). Kaplan-Meier analysis will be repeated in the subgroup of patients who received a starting dose of 125mg.

One Cox regression analysis will be generated for each time to event endpoint, provided the sample size supports the analysis. Demographic and baseline clinical characteristics, some examples are detailed in section 7.1, will be included to the extent that sample size permits. Results from this analysis results will include parameter estimates, p-values, standard errors, hazard ratios and 95 % CIs of hazard ratios. The proportional hazards assumption will be assessed graphically with the inspection of Schoenfeld residuals and by including interaction terms between the variables and log(time).

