Breast cancer histology	List captured at initial breast cancer diagnosis including: Adenoid cystic; Cribriform; Ductal; Inflammatory; Intraductal; Lobular; Medullary with lymphoid stroma; Medullary, NOS; Mucinous; Paget's disease and infiltrating; Paget's disease and intraductal; Papillary; Secretory; Squamous cell; Tubular, and more
ECOG/KPS performance score	Score captured on date closest to (with a ± 60 day cutoff around) 1) A/MBC diagnosis; and 2) initiation of palbo
Stage at initial BC diagnosis	0, I, IA, IB, II, IIA, IIB, III, IIIA, IIIB, IIIC, IV, Unable to stage, Not found, Not applicable
Presence of distant metastasis	
Yes; No
 
Note: this variable would be "yes" if patient is diagnosed with de novo metastatic breast cancer or if patient developed metastasis after initial breast cancer diagnosis

Date of first distant metastasis	Same as initial BC diagnosis if de novo metastatic BC, otherwise captured as date that the patient developed distant metastatic disease
Site(s) of distant metastasis at MBC diagnosis	
Bone; Chest Wall; Contralateral Breast; Distant Lymph node(s); Liver; Lung; Peritoneum; Pleural nodules; Malignant pleural effusion; Skin; Brain (brain and spinal metastases); Ovary; Undocumented; Other, Specify;
 
Visceral sites (Liver, Lung, Peritoneum and Pleural nodules);

PFIZER CONFIDENTIAL

	Bone only
Comorbidities	List of comorbidities at time of A/MBC diagnosis (sourced from problem list encompassing entire patient journey and confirmed from clinician notes), including: anemia, heart arrhythmia, hypertension, myocardial infarction, congestive heart failure, peripheral vascular disease, cerebrovascular accident, hemiplegia, chronic obstructive pulmonary disease, ulcer disease, diabetes with chronic complications, diabetes without chronic complications, renal disease, connective tissue disease such as rheumatoid arthritis or lupus, Alzheimer's or other dementia, cirrhosis or other serious liver disease, non-breast cancer malignancy (excluding sites of breast cancer metastasis and malignant neoplasm of skin), metastatic solid tumor (other than breast cancer), HIV/AIDS, and other comorbidities of interest
Note: comorbidities in bold are in CCI; CCI listed in derived variables section	
Biomarkers	
ER, PR, HER2 status	Positive; Negative; Equivocal; Unknown

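### The Cox shell gives de novo patients no level in the time-to-metastasis row, so with the metastatic group and Stage IV rows alongside it the de novo hazard ratio is mislabelled or close to non-identified

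*SAP*

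**What the plan says.** Three rows of the rwOS Cox shell (SAP Section 8.2.1, Table 15.2.1.3) matter here:

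- "Metastatic group (de novo vs recurrent"
- "Time from initial diagnosis to metastasis (≤ 36 vs > 36 months"
- "Stage at Diagnosis (IV vs 0 or I"

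Section 7.2 puts them in a single model: "One Cox regression analysis will be generated for each time to event endpoint, provided the sample size supports the analysis". Section 8.2.1 allows the same shell to be reused for rwPFS, rwTTD, rwTTNT, rwTTC and rwTTDA.

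Elsewhere the SAP treats de novo disease differently. On time to metastasis, Section 5.1 says: "It will be categorized into ≤12 months, 13-24 months, 25-36 months,>36 months and de novo metastatic". Table 15.1.3 repeats those five categories. For the date of first distant metastasis, Appendix 2 (Section 9.2) says: "Same as initial BC diagnosis if de novo metastatic BC, otherwise captured as date that the patient developed distant metastatic disease". Section 7.1 lists a further covariate, "metastatic status (De novo, versus number of metastatic sites".

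The eligibility criteria in Section 4 admit stage IIIB and IIIC disease as well as stage IV or distant metastasis. No section says which level of the 36-month row a de novo patient takes.

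**The concern.** A patient who is metastatic at first diagnosis cannot have a time to metastasis above 36 months. One cell of the cross-classification of metastatic group by time to metastasis is therefore empty by construction. Adjusting one row for the other needs overlap that does not exist. The coefficient on the de novo row depends on a coding decision that the SAP leaves open, and the printed label would not tell a reader which comparison was made.

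The Stage IV row adds to this, because stage IV at initial diagnosis and de novo metastatic disease are nearly the same set of patients. The Section 7.1 wording does not help: de novo status and number of metastatic sites are not mutually exclusive. Eligible stage IIIB/IIIC patients without distant metastasis have no time to metastasis, and are neither de novo metastatic nor recurrent-metastatic.

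At stake is how two prognostic contrasts are read: de novo against recurrent, and early against late relapse.

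**Working it through.** The SAP gives no figure for this model, so there is nothing to reproduce. The check is algebra on the rows, followed by an illustration with assumed inputs.

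**Step 1. De novo coded 0 months (Appendix 2 date rule), stage rows ignored.** Let D = 1 for de novo and E = 1 for time ≤36 months. The log hazard relative to late relapse is b_D·D + b_E·E:

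- recurrent >36 months: 0
- recurrent ≤36 months: b_E
- de novo: b_D + b_E

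So exp(b_D) = h_de novo / h_early. The comparator is relapse within 36 months, not all recurrent patients. The ≤36 row itself, exp(b_E) = h_early / h_late, is correct under this coding.

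**Step 2. De novo given no value in the row (one reading of Section 5.1), complete-case fit.** Every de novo patient drops out, the de novo column is constant (rank 1 of 2), and its hazard ratio cannot be estimated. With an assumed 30-50% de novo, and the 300-400 patients expected in Section 2.1, the loss would be 90-150 of 300 or 120-200 of 400.

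**Step 3. De novo as a third level of the row.** The level duplicates the metastatic group row exactly (rank 2 of 3). If the duplicate is dropped, what remains is de novo against late relapse.

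**Step 4. Add the stage rows, de novo coded 0 months.** If initial stage IV and de novo coincide, the metastatic group, stage and time rows together have rank 4 of 5. The de novo coefficient is then not identified; if the two only nearly coincide, it is very imprecise. If software drops the Stage IV column, de novo patients fall into the stage reference, and the comparator narrows to early relapse from initial stage 0 or I.

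**Step 5. Illustrative size for Step 1.** The assumptions, none from the SAP, are hazards of 0.9 for de novo, 1.5-2.2 for early relapse and 1.0 for late relapse, an early share p of 20-40% among recurrent patients, and no stage rows.

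- Row as fitted: h_de novo / h_early
- Contrast named by the label, approximately: h_de novo / (p·h_early + 1 − p)

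| h_early | p | Row as fitted | De novo vs all recurrent |
|---|---|---|---|
| 1.5 | 0.2 | 0.9/1.5 = 0.60 | 0.9/1.10 = 0.82 |
| 1.5 | 0.4 | 0.60 | 0.9/1.20 = 0.75 |
| 2.2 | 0.2 | 0.9/2.2 = 0.41 | 0.9/1.24 = 0.73 |
| 2.2 | 0.4 | 0.41 | 0.9/1.48 = 0.61 |

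The averaging formula in the last column is an approximation. At 0.9 de novo, 1.8 early relapse, 1.0 late relapse and p = 0.3, it gives 0.9/(0.3·1.8 + 0.7) = 0.9/1.24 = 0.73, where a simulated Cox fit gave 0.76.

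**Step 6. Check by simulation.** Two-row Cox fits of 20,000 patients used a de novo hazard equal to late relapse and an early-relapse hazard of 1.5 or 2.0. The de novo row gave 0.64-0.67 and 0.50-0.52 respectively. The metastatic group row alone gave 0.82-0.91 and 0.76-0.91. A single three-level factor recovered de novo against late relapse at 0.97-1.04 (true 1.0) and early against late at 1.46-1.52 (true 1.5) or 1.98-2.01 (true 2.0), with no patient dropped. These fits had no stage rows.

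**The case against.** The strongest reply is that the model is discretionary and descriptive. Section 7.1 says only that covariates may be included, as data and sample size allow. Section 3 states no hypotheses, and the shells are templates. This stands as a limit on severity. A reader might infer that all six endpoints will carry a wrong hazard ratio. The SAP does not support that, because the fault arises only when these rows enter together. But that is what the shell displays.

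A second reply is that Appendix 2 supplies a date and not a coding, and that Section 5.1 keeps de novo outside the month categories. This is fair. It means that neither the early-relapse comparator nor the loss of patients is fixed by the text. The loss also needs complete-case fitting, which the SAP does not specify: Section 6 would place absent data in a not-documented category, although the shell has no such row. It does not rescue the label, since none of the codings examined gives de novo against all recurrent with both rows present.

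Third, the figures come from a model without stage. This also stands. A reader might take 0.41-0.60 as what the shell would report, but with the Stage IV row in the model the coefficient may not be identified at all.

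Finally, one might infer that the rwPFS analysis by metastasis status is compromised. It is a Kaplan-Meier analysis and does not depend on this Cox coding.

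**Conclusion.** The shell is wrong as written and should be fixed, though it does not threaten the study's main descriptive results. With the metastatic group and time-to-metastasis rows both in the model, the de novo hazard ratio is mislabelled, aliased or not estimable, depending on an unstated coding. The Stage IV row brings it close to non-identified under any of these codings. Eligible stage IIIB/IIIC patients without distant metastasis have no level in either of the first two rows.

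The change of comparator under the 0-month coding follows from the structure of the rows. Its size does not: about 0.41-0.60 against about 0.61-0.82 rests wholly on assumed hazards and shares, with stage left out. Kaplan-Meier medians and landmark estimates are unaffected.

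**What to change.** In the Cox shell and in Section 7.1:

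1. Replace the metastatic group and time-to-metastasis rows with one mutually exclusive factor: recurrent >36 months (reference), recurrent ≤36 months, de novo metastatic, and locally advanced without distant metastasis. Merge the last level, or only describe it, if it is sparse.
2. Remove the separate Stage IV level, so that initial stage is contrasted only among patients who are not de novo. One way is to code de novo patients to the stage reference level and say so in a footnote, which should add that the de novo row is then read against late relapse at that reference stage.
3. Label the de novo row as de novo against recurrent >36 months. If de novo against all recurrent is wanted, report it from a model without the time-to-metastasis term.
4. Delete the Section 7.1 covariate that sets de novo against number of metastatic sites.

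The Kaplan-Meier subgroup by metastasis status need not change. The cost is SAP wording and one shell, with no new data.

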8.2.2 Safety Data

Not applicable

8.2.3 Medication/ Treatment Data

Treatment Patterns

PFIZER CONFIDENTIAL

[figure not shown]

Table 15.4.1. Total Number of Lines Per Patient from the Diagnosis of A/MBC

Variable, n (%)	palbociclib + AI (n=xxx)
1	n (x.x%)
2	n (x.x%)
3	n (x.x%)
4	n (x.x%)
≥5	n (x.x%)

Table 205.4.2. Treatments by Line of Therapy from the Diagnosis of A/MBC

Line	Regimen (Agents)	palbociclib + AI (n=xxxx)
1 (N=xxx)	XXXXXX	n (x.x%)
	XXXXXX	n (x.x%)
	XXXXXX	n (x.x%)
	...	
2 (N=xxx)	XXXXXX	n (x.x%)
	XXXXXX	n (x.x%)
	XXXXXX	n (x.x%)
	...	
3 (N=xxx)	XXXXXX	n (x.x%)
	XXXXXX	n (x.x%)
	XXXXXX	n (x.x%)
	...	
	XXXXXX	n (x.x%)
4 (N=xxx)	XXXXXX	n (x.x%)
	XXXXXX	n (x.x%)
	XXXXXX	n (x.x%)
	...	
5 (N=xxx)	XXXXXX	n (x.x%)
	XXXXXX	n (x.x%)
	XXXXXX	n (x.x%)
	...	

Figure 215.4.3. Proportion of Patients with Regimen by Line of Therapy from the Diagnosis of A/MBC

PFIZER CONFIDENTIAL

Dosing Description

Table 15.4.4. Dosing at Start and End of Treatment, n (%)

Starting dose	End dose				
	75mg	100mg	125mg	Unknown	Total
75 mg	n (x.x%)				
100 mg	n (x.x%)				
125 mg	n (x.x%)				
Unknown	n (x.x%)				
Total	n (x.x%)				

Table 15.4.5. Dosing description

Variable/Statistic	palbociclib + AI (n=xxx)
Dose adjustment	
No adjustment	n (x.x%)
Increase	n (x.x%)
Decrease	n (x.x%)
Unknown	n (x.x%)
Type of dose adjustment	
Hold	n (x.x%)
Schedule change	n (x.x%)
Dose delay	n (x.x%)
Hold	n (x.x%)
Cost	n (x.x%)
Patient refusal	n (x.x%)
Toxicity	n (x.x%)
Time (days) to Dose Adjustment	
n	xx
Mean (SD)	x.x (x.xx)
Median (Q1, Q3)	x.x (x.x, x.x)
Min, Max	x.x, x.x
Discontinuation	
No	n (x.x%)
Yes	n (x.x%)
Discontinuation reason	
Progression	n (x.x%)
Intolerance/Toxicity	n (x.x%)
Other/Unknown	n (x.x%)
Patient choice	n (x.x%)
Treatment for other diseases	n (x.x%)
Left health system	n (x.x%)
End of planned therapy	n (x.x%)
Changes in insurance	n (x.x%)
Death	n (x.x%)
Hospice referral	n (x.x%)

PFIZER CONFIDENTIAL

[figure not shown]
Table 15.4.5. Dosing description

Variable/Statistic	palbociclib + AI (n=xxx)
Physician choice	n (x.x%)
Treatment ongoing	n (x.x%)

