2.1 Study Design

[figure not shown]
This is an observational, retrospective cohort study. Eligible patients will be identified from the Syapse Learning Health Network database and medical chart review will be conducted by Syapse Certified Tumor Registrars (CTRs). All study data are secondary data and will have been collected retrospectively from existing clinical data originally collected as part of routine care. This single-arm descriptive analysis will describe the patient characteristics, clinical attributes and treatment patterns of A/MBC patients with HR+/HER2- disease, who were treated with palbociclib + AI as first-line therapy. Additionally, clinical effectiveness outcomes for these patients will be evaluated between Feb 2015 and July 2019.

Study population

The study will include adult patients 18 years or older, diagnosed with HR+/HER2- A/MBC who initiated palbociclib combination therapy with AI as the first-line therapy on or after 03 February 2015 up to and including 31 July 2019. Patients for this study will be identified from the Syapse Learning Health Network database.

Preliminary analysis identified up to 1,074 patients with evidence of key primary inclusion criteria: breast cancer diagnosis and palbociclib treatment. Three to four hundred patients are expected to fulfil complete study inclusion criteria. Given the inclusion criterion requiring a qualifying treatment identification period between 03 February 2015 through 31 July 2019, and assuming a data cutoff date of 01 February 2020, the minimum follow-up available is therefore 6 months.

PFIZER CONFIDENTIAL

Data source

Patients will be identified and data will come from the Syapse Learning Health Network database which includes both inpatient and outpatient clinical and molecular data captured through manual abstraction and interoperative data feeds from a number of health system source systems, including:

- *Electronic medical record (EMR), including inpatient, outpatient oncology, ambulatory, surgical, etc.*
- *Electronic data warehouse (EDW)*
- *Laboratory information system (LIS)*
- *Picture archiving and communication system (PACS)*
- *Hospital based cancer registries*
- *Computerized physician order entry (CPOE)*

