7.2 Statistical Analyses

Objective1:

- a. To describe the demographic and clinical characteristics for patients diagnosed with HR+/HER2- A/MBC.

[figure not shown]
The numbers of breast cancer patients in the Syapse database meeting the eligibility criteria will be presented in an attrition table.

Demographic and clinical characteristics variables that will be reported include age, sex, race, insurance status, menopausal status, and region of residence at A/MBC diagnosis, stage of initial diagnosis, histology, Eastern Cooperative Oncology Group (ECOG) performance status (where ECOG score unavailable, Karnofsky performance status will be converted to corresponding ECOG score) and comorbid disease burden, HER2 and estrogen receptor (ER)/ progesterone receptor (PR) status, BRCA status, number and sites of distant metastasis at A/MBC diagnosis; modalities of treatment received prior to A/MBC diagnosis (chemotherapy, hormone therapy, surgery, radiation therapy), disease free interval (time between completion of adjuvant therapy and diagnosis of A/MBC) and follow-up time in the study. Descriptive analysis methods as detailed in Section 7.1 will be used for summarizing these parameters as appropriate.

- b. To describe the treatment patterns for patients diagnosed with HR+/HER2- A/MBC.

Treatment patterns generally include the record of all systemic anti-cancer therapies received from the index date through the end of the study period.

CCI

Description will include each of the following.

- Distribution of regimens, with the frequency and percentage of patients receiving each regimen within each line from the diagnosis of A/MBC through the end of the record.
- Description of sequence of regimens across lines, which shows how individual regimens were sequenced across lines through the end of the record of systemic therapy. Description will include the frequency and percentage of patients who received each specific sequence of treatments.
- Description of the dosing will include the starting dose, end dose, dose adjustment (dose increase and dose reduction), type of dose adjustment (dose modification, schedule changes, dose delay or hold), discontinuation reason (including death, progression, end of planned therapy, insurance changes, schedule change, dose delay, hold, cost, patient refusal, toxicity), and time to dose adjustment.

Objective2:

To examine clinical effectiveness for patients diagnosed with HR+/HER2- A/MBC.

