7.2.2 Summary of Analyses of the Study Outcomes

Outcome	Analysis Set	Supports Protocol Objective Number	Subgroup	Statistical Method	Factors/Covariates/Strata	Missing Data
Summary of Demographic Characteristics	All patients meeting inclusion and exclusion criteria	1a	None	Frequency and percentage of subjects	Not Applicable	Numbers reported
Summary of clinical characteristics and comorbidities	All patients meeting inclusion and exclusion criteria	1a	None	Frequency and percentage of subjects	Not Applicable	Numbers reported
Treatment pattern	All patients meeting inclusion and exclusion criteria	1b	None	Frequency and percentage of subjects	Not Applicable	Numbers reported
Treatment Regime	All patients meeting inclusion and exclusion criteria	1b	None	Frequency and percentage of subjects	Not Applicable	Numbers reported
Time to rwOS, months	All patients meeting inclusion and exclusion criteria	2	125mg starting dose	Kaplan-Meier and Cox proportional hazards model	Factors defined in section 7.1	Censored
Time to rwPFS, months	All patients meeting inclusion and exclusion criteria	2	- Metastasis status - 125mg starting dose	Kaplan-Meier and Cox proportional hazards model	Factors defined in section 7.1	Censored
Time to rwTTD, months	All patients meeting inclusion and exclusion criteria	2	125mg starting dose	Kaplan-Meier and Cox proportional hazards model	Factors defined in section 7.1	Censored

PFIZER CONFIDENTIAL

CCI

Time to rwTTNT, months	All patients meeting inclusion and exclusion criteria	2	125mg starting dose	Kaplan-Meier and Cox proportional hazards model	Factors defined in section 7.1	Censored
Time to rwTTC, months	All patients meeting inclusion and exclusion criteria	2	125mg starting dose	Kaplan-Meier and Cox proportional hazards model	Factors defined in section 7.1	Censored
Time to rwTTDA, months	All patients meeting inclusion and exclusion criteria	2	125mg starting dose	Kaplan-Meier and Cox proportional hazards model	Factors defined in section 7.1	Censored

PFIZER CONFIDENTIAL

CCI

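### Lines per patient and treatment sequences are planned as crude percentages over follow-up of about 6 to 60 months, so they refer to no fixed horizon and mix different outcomes in one row

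*SAP*

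**What the plan says.** Section 2.1 admits patients who start first-line palbociclib plus an AI "on or after 03 February 2015 up to and including 31 July 2019". It reasons, "assuming a data cutoff date of 01 February 2020", that "the minimum follow-up available is therefore 6 months". The expected cohort is 300 to 400 patients.

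For Objective 1b, Section 7.2 plans "Distribution of regimens, with the frequency and percentage of patients receiving each regimen within each line". For sequences across lines it adds: "Description will include the frequency and percentage of patients who received each specific sequence of treatments". The summary in Section 7.2.2 lists frequency and percentage as the only method for treatment pattern, with no subgroup or stratum.

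In Section 8.2.3, the shell "Table 15.4.1. Total Number of Lines Per Patient from the Diagnosis of A/MBC" has rows 1, 2, 3, 4 and ≥5, each as n (%) of the whole cohort, with no split by status at the end of the record. The treatments-by-line shell differs: each line has its own N.

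The nearest time-to-event analysis is rwTTNT (Sections 5.1 and 7.2). It runs from first-line start, counts a next line or death as the event, and censors other patients at last contact or study end. Its landmarks run from 3 to 36 months.

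**The concern.** How many lines are recorded for a patient depends on how long the patient could be observed, and here that is set by the start date. A patient who started in July 2019 has had little time to reach a second line; one who started in February 2015 has had almost five years. A single percentage over both is an average over whatever mix of start dates the cohort has. It would change if the cutoff moved, even if practice did not.

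The '1 line' row also pools patients for whom one line means different things: still on first line, died before a second, ended first line with no further therapy, or out of contact. A sequence consisting only of palbociclib plus an AI has the same ambiguity.

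The sequence of regimens is part of a primary objective. A reader may take these figures as the share of patients who go on to later therapy, or set them beside another cohort with different follow-up. The SAP censors all six time-to-event outcomes but does nothing comparable for line counts and sequences drawn from the same incomplete records.

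**Working it through.** **1. Follow-up, from the SAP's dates (30.4375 days per month).**
- Last eligible start, 31 Jul 2019, to 01 Feb 2020: 185 days = 6.08 months. This reproduces the SAP's 6 months.
- First eligible start, 03 Feb 2015, to 01 Feb 2020: 1,824 days = 59.93 months.
- Length of the start window: 59.93 − 6.08 = 53.85 months.
- If starts are uniform (assumption), the share with at least m months of potential follow-up is (59.93 − m)/53.85: 89% at 12, 67% at 24 and 44% at 36 months.

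These are potential times. Actual follow-up can be shorter through death or last contact.

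**2. Illustration.** The SAP gives no rate of next therapy, death or loss, so the following are assumptions: exponential time to next line or death with median 24 months, 15% of those events being death without a second line, uniform starts, no loss to contact.
- Hazard h = ln 2/24 = 0.02888 per month.
- Cumulative incidence of a second line: F(t) = 0.85 × (1 − exp(−h t)).
- F(12) = 0.85 × (1 − 0.7071) = 24.9%; F(24) = 0.85 × 0.5 = 42.5%; F(36) = 0.85 × (1 − 0.3536) = 55.0%.
- Crude share with ≥2 lines is F averaged over follow-up from a = 6.08 to b = 59.93: 0.85 × {1 − [exp(−h a) − exp(−h b)]/[h(b − a)]} = 0.85 × {1 − (0.8390 − 0.1772)/1.5552} = 0.85 × 0.5744 = 48.8%.

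**3. Dependence on start date and cutoff, practice held fixed.**
- Starters in 2015: 67%. Starters in 2019: 20%.
- Cutoff 12 months later (follow-up 18.08 to 71.93 months): 59%.

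**4. Other medians, same remaining assumptions.**

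| Median (months) | Crude ≥2 lines | 12 months | 24 months | 36 months |
|---|---|---|---|---|
| 18 | 57% | 31% | 51% | 64% |
| 24 | 49% | 25% | 42.5% | 55% |
| 30 | 43% | 21% | 36% | 48% |

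In each row the crude figure lies above the 12- and 24-month values and below the 36-month value, so it estimates none of them.

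**5. What the other planned outputs cover.** rwTTNT handles censoring for the first transition, but it counts death as an event, so it does not estimate second-line uptake, and it stops at second line. No planned analysis handles censoring for third or later lines or for sequences.

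**The case against.** The study is single-arm and descriptive, with no hypotheses, and the SAP says sequences are described to the end of the record. Observed counts answer that aim, and Objective 1b does not ask what share would eventually reach a later line. This stands: the counts are legitimate and should stay.

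Part of the missing split can be recovered. Section 7.2 reports numbers of events and censored patients for each Kaplan-Meier analysis. rwTTNT events minus patients with ≥2 lines therefore gives deaths before second line, and the censored count gives those without a recorded next line or death. Table 15.4.5 has rows for ongoing treatment, death, leaving the health system and hospice referral, and Table 15.1.9 gives follow-up times. This also stands, but only for first line. The censored count still mixes patients on treatment, patients who stopped and patients out of contact, and neither table is crossed with number of lines.

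Regimen percentages within a line use that line's own N, so the arithmetic above does not apply to them.

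A reader might infer two stronger claims:
- **That '1 line' mostly means still in first line at cutoff.** The SAP supplies no rates from which to derive this. Over 60 assumed scenarios (median 12 to 36 months, death 10 to 30% of events, loss 0 or 10% per year, starts uniform or weighted to later dates), the share of that row still event-free and in contact at cutoff ran from 36% to 95%. Event-free patients also include those who stopped first line and are alive without a next line.
- **That later-line use is simply understated.** This depends on the horizon. In the illustration the crude 49% exceeds the 12- and 24-month values and falls below only the 36-month one. A 60-month comparison is not usable, because the longest potential follow-up is 59.9 months and the SAP's landmarks stop at 36.

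**Conclusion.** The point holds as a minor reporting improvement. From the SAP alone it follows that line counts and sequences are crude percentages of the whole cohort, that potential follow-up runs from 6.1 to 59.9 months, that the '1 line' row combines different outcomes, and that no censoring-aware estimate is planned beyond the first transition. The percentages therefore have no fixed horizon and move with start dates and cutoff.

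The size rests on assumed rates. In the central illustration, start year alone moves the crude share with ≥2 lines between 67% and 20%, and a 12-month later cutoff raises it from 49% to 59%. The documents support neither a fixed direction of bias nor a claim about which group dominates the '1 line' row. No effectiveness result is affected.

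**What to change.** - Keep the counts in Table 15.4.1 and in the sequence description, and label them as observed to cutoff.
- Split each line row by status at end of follow-up: on that line, died, ended the line with no further therapy, or last contact before cutoff.
- Add the Aalen-Johansen cumulative incidence of starting second line from first-line start, and of third line from second-line start. Treat death without a further line as the competing event, and report at 12, 24 and 36 months where numbers at risk allow.

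Appendix 2 already lists line start and end dates, date of death and last contact date, so no new data are needed. The cost is some SAP wording, a few table rows and one estimate per transition. The downsides are slightly longer tables and imprecise third-line estimates in a cohort of 300 to 400.
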